7.0 STUDY POPULATION

7.1 Inclusion Criteria

Individuals participating in the clinical trial must:

- 1) Be at least 18 years old.
- 2) Be willing and able to provide written informed consent and HIPAA Authorization (if applicable) for medical record abstraction.
- 3) Meet DSM-5 criteria for moderate or severe opioid use disorder.
- 4) Be willing to be randomized to antagonist-based therapy or TAU.
- 5) Have an HIV viral RNA count > 200 copies/ml. HIV viral RNA may be drawn with screening blood draw or abstracted from medical records if drawn in the 90 days prior to the date of consent.
- 6) Be willing to establish ongoing HIV care at the site if not already receiving ongoing care.
- 7) If female, be willing to take at least one evidence-based measure to avoid becoming pregnant.

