9.1.3 Screening and Enrollment Procedures (1-4 weeks duration)

Once a person has completed the Pre-Screening Interview process and meets basic eligibility criteria, they will either be asked to stay for the Screening Visit or scheduled to come back for the visit (based on staff and candidate's availability). It is expected that the screening and enrollment phase will take approximately 1-4 weeks; however, participants will have 60 days from the date of consent to complete screening and be randomized before being considered a screen failure.

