9.1.6 Medical Record Release Form

Participants will complete the form(s) as applicable during screening and throughout the study to grant permission to study staff to review inpatient, outpatient, mental health, and substance use treatment clinic records as needed. The purpose of medical record review at the end of study participation is to document information needed to evaluate secondary outcomes. Specifically, study staff will abstract medical record information to corroborate participants' self-report of information including, but not limited to the following: HIV viral load and CD4 count, liver enzymes, hepatitis B and C serologies, CBC, metabolic panel, INR, utilization of HIV primary care, utilization of HIV and addiction treatment services, and opioid overdose events. Records review/abstraction will occur throughout the study (as needed) and up to 52 weeks post-randomization.

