9.1.7 Collection of Biological Specimens

Study staff will collect blood specimens at screening, randomization, 12 weeks, and 24 weeks to confirm eligibility and assess the primary outcome of HIV-1 RNA PCR and secondary outcomes of CD4 count, VACS Index, and hepatotoxicity. CBC, serum creatinine, LFTs (AST, ALT), INR, and HIV-1 RNA blood specimens will be collected during screening. CD4, Hepatitis C, Hepatitis B, and PBMC specimens will be collected and processed only after the participant has been randomized. Study staff will collect urine specimens during screening and at treatment initiation (XR-NTX arm only), safety visit (XR-NTX arm only), and at 4, 8, 12, 16, 20, and 24 weeks to confirm eligibility and assess secondary outcomes and pregnancy. Screening and randomization labs (CD4, HIV-1 RNA, and hepatitis B and C serologies) drawn in the 90 days prior to date of informed consent may be abstracted from participant medical records, when available. Other screening lab tests may be abstracted from medical records if drawn within 30 days prior to the date of informed consent, with the exception of urine specimens, which must be collected by study personnel. Some participating sites may require that copies of some or all lab results collected for study purposes be filed in participants' medical records.

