12.0 GENERAL MEASURES

12.1 Inclusion/Exclusion

This form will include each inclusion and exclusion criterion to document eligibility. Eligibility will be assessed prior to randomization, and then continually as appropriate. Only participants who continue to meet study eligibility criteria will be allowed to continue with the screening process and randomization.

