13.5 Clinical Laboratory Tests

Trained staff will be responsible for collecting and processing biologic specimens. Local laboratories at participating sites will be used to conduct all laboratory tests with the exception of the PBMCs. Laboratories must participate in the Clinical Laboratory Improvement Act of 1998 (CLIA) or be accredited by the College of American Pathologists (CAP). If neither CLIA nor CAP is available, equivalent evidence of laboratory certification may be acceptable and must be discussed on a case-by-case basis with the Lead Team. Laboratories should provide reference ranges and proof of laboratory certification.

HIV-1 RNA PCR: will be drawn at screening, 12, and 24 weeks (or the end of study visit, if not week 24) for outcomes assessment. At screening, results of laboratory tests conducted within 90 days prior to date of informed consent will be acceptable.

CD4 Count (T-helper cells): will be drawn at randomization and at 12 and 24 week visits or the end of study visit, if not week 24, for secondary outcomes assessment. At randomization, results of laboratory tests conducted within 90 days prior to date of informed consent will be acceptable.

Peripheral Blood Mononuclear Cells (PBMCs): For all randomized participants (both TAU and XR-NTX), we will collect four 8mL or eight 4mL CPT tubes for PBMC analysis at randomization,

12, and 24 (or end of study visit if not week 24). Blood draws may coincide with other research blood draws. PBMC analysis will be conducted in a related NIH application to assess the effects of opioid blockade on TLR mediated immune responses at a later time. PBMC samples will be shipped to a lab at Oregon Health & Science University and kept indefinitely. PBMC samples will be used for immunologic testing. It is also possible that banked PBMC specimens will be shared with other investigators for performance of genetic testing in the future.

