As remarked above, the Random Assignment Bootstrap approach has its own limitations. Some arise from the small size of the pilot study. Others have to do with differences in pilot study and scale-up designs. Specifically, the proposed scale-up will have VL visits at months 0, 3, and 6, with the primary suppression outcome being assessed at M6. The pilot study had visits at months 0, 1, 2, 3, and 4, but in this simulation we use only visits 0, 2, and 4 to assess the outcome at M4. The pilot study design is less powerful than the scale-up will be because although it has the same number of visits, they are temporally closer together. Also, if there is an outcome difference between arms in CTN0055, random assignment bootstrapping will probably over-estimate the within-arm variance, leading to a smaller power estimate. For these reasons, scale-up power is expected to exceed the power calculated by Random Assignment Bootstrapping of the pilot study.

The power calculations are performed only for the members of the opiate-only + overlap group who are unsuppressed at baseline. There are only 9 participants in this group, with suppression status values at the various visits as given in Table 2.

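### Does a qualifying viral load that may be up to 150 days old at randomization undermine the non-inferiority comparison?

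*Combined protocol and SAP*

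**What the plan says.** Section 7.1, criterion 5, takes the qualifying HIV-1 RNA either from the screening draw or from the chart, where it may be "abstracted from medical records if drawn in the 90 days prior to the date of consent". Sections 9.1.7 and 13.5 repeat the 90-day window. Section 9.1.3 expects screening to last 1 to 4 weeks, but "participants will have 60 days from the date of consent to complete screening and be randomized before being considered a screen failure".

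On timing, Section 13.5 states: "HIV-1 RNA PCR: will be drawn at screening, 12, and 24 weeks". The Section 10.1 schedule likewise has an HIV-1 RNA entry at screening and none at randomization. Section 9.1.7 also puts HIV-1 RNA in screening and says "CD4, Hepatitis C, Hepatitis B, and PBMC specimens will be collected and processed only after the participant has been randomized", but later in the same paragraph it groups "Screening and randomization labs (CD4, HIV-1 RNA, and hepatitis B and C serologies) drawn in the 90 days prior to date of informed consent" as results that may be taken from records. Appendix C says "the proposed scale-up will have VL visits at months 0, 3, and 6".

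Section 12.1 provides that "Only participants who continue to meet study eligibility criteria will be allowed to continue with the screening process and randomization", without attaching a repeat test.

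The primary model in Section 17.2 uses months 3 and 6 only, with treatment, month, their interaction, baseline alcohol use disorder and site. The sensitivity analyses in Sections 17.2 and 17.10 concern missing data, treatment received and a per-protocol comparison.

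**The concern.** The trial enrols unsuppressed patients for a stated reason. Section 4.3 reports that 80% of pilot participants were suppressed at baseline, and warns that including such participants in a non-inferiority trial favours the non-inferior conclusion and weakens assay sensitivity. A chart value several months old does not guarantee that the participant is still unsuppressed on the day of allocation. Section 6.3 notes that nearly everyone who starts antiretroviral therapy can now reach 200 copies/ml or less within 6 months, and it allows for participants who are already on therapy at enrolment.

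If some participants are suppressed at randomization and stay so in both arms, they add equal successes to each side and move the risk ratio toward 1. A non-inferior result would then say less about patients who were truly unsuppressed, and the plan names no analysis to check this. The safety laboratory tests have a 30-day look-back, yet the variable that defines the population has 90. The mixed wording about a month-0 viral load makes it harder to see what the baseline value is. The VACS Index adds to this: Section 11.4 says it is assessed at randomization, while Section 8.2 derives it from screening laboratory data.

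**Working it through.** **Age of the qualifying value.** Chart value, both limits used in full: 90 + 60 = 150 days. Chart value at the upper end of expected screening: 90 + 28 = 118 days. Screening draw: at most 60 days.

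**The plan's own figure.** Section 17.1 claims at least 80% power with 175 per arm and a margin of 0.75. It comes from bootstrapping nine pilot participants, whose visit-level data are not in the text I have, so I cannot reproduce it exactly. A log risk ratio approximation with equal arms gives

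power = Φ( −ln 0.75 / √[2(1−p)/(175p)] − 1.96 ).

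At p = 0.52 this is Φ(0.2877/0.1027 − 1.96) = 80.0%. At p = 0.57, the TAU rate used for the margin in Section 17.7, it is Φ(0.2877/0.0929 − 1.96), about 87%. The approximation is consistent with the plan and can be used below.

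**Effect of already-suppressed participants.** Let f be their share, s their week-24 suppression rate under TAU, and r their XR-NTX to TAU risk ratio. Among the rest, take TAU = 0.57 and a true risk ratio of 0.75, the edge of the margin. Then

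- pT = (1−f)·0.57 + f·s
- pN = (1−f)·0.57·0.75 + f·s·r
- SE = √[(1−pT)/(175pT) + (1−pN)/(175pN)]
- P(declare non-inferiority) = Φ( [ln(pN/pT) − ln 0.75]/SE − 1.96 )

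Worked case, f = 0.10, s = 0.9, r = 1: pT = 0.513 + 0.090 = 0.603; pN = 0.38475 + 0.090 = 0.47475; ratio 0.787; SE = 0.1004; Φ(0.4835 − 1.96) = 7.0%.

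| Assumption for the already suppressed | f = 0 | 1% | 5% | 10% |
|---|---|---|---|---|
| s = 0.90, r = 1 | 2.50% | 2.79% | 4.28% | 6.99% |
| s = 0.75, r = 1 | 2.50% | 2.74% | 3.93% | 5.96% |
| s = 0.90, r = 0.82 | 2.50% | 2.58% | 2.92% | 3.40% |
| s = 0.90, r = 0.75 | 2.50% | 2.50% | 2.50% | 2.50% |

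The 0.75 in row 2 is 0.9 × (1 − 6/36), which counts the pilot's missing rate (Section 9.2.3.3) as unsuppressed. The 0.82 in row 3 is the pilot's week-16 figures for participants with alcohol use disorder, 82% against 100% (Section 4.3), a small group and a different population. In row 1 the true risk ratio of the enrolled population is 0.754, 0.769 and 0.787 at f = 1%, 5% and 10%. It lies above the margin, so for that population a non-inferior finding is correct.

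**A rough guide to f.** The documents do not give it. Section 17.7 assumes about 15% suppression without treatment for opioid use disorder. Suppose, as an illustration, that this accrues evenly over 24 weeks (168 days), that chart values are spread evenly over 90 days (mean 45), and that screening takes about 17 days. Then f = 0.15 × 62/168 = 5.5% if everyone qualifies on a chart value, 2.8% if half do and 1.4% if a quarter do, treating screening draws as current. Row 1 then gives 4.5%, 3.4% and 2.9%.

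**The month-0 wording.** Section 13.5, the Section 10.1 schedule and the first mention in Section 9.1.7 all place HIV-1 RNA at screening. The later list in Section 9.1.7 reads naturally as pooling the screening test with the tests taken after randomization. Appendix C's month 0 is shorthand in a power discussion. The primary model has no month-0 record.

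**The case for a change.** The strongest case for acting is that the sponsor raised this bias itself, that the remedy looks cheap, and that the data largely exist. The draw date is needed to apply the 90-day rule, and under Section 9.1.6 "Records review/abstraction will occur throughout the study (as needed) and up to 52 weeks post-randomization". One sentence in Section 17.10 could restrict the primary model to participants whose last value before randomization was recent and above 200. Because it would use only pre-randomization values, it would introduce no post-randomization selection. In the pilot, 5 of the 9 unsuppressed participants with opioid use disorder were suppressed at their last non-missing value, so status can change within months.

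The facts stand: 150 days is permitted, no fresh value is required, and no planned analysis looks at it. The inference to a needed change does not. The pilot participants were in a treatment trial, so 5 of 9 is not an estimate of f. The Section 4.3 warning concerned a pilot that enrolled regardless of viral load, and requiring an unsuppressed value was part of the response to it.

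The restricted analysis would drop many people who are still unsuppressed along with any who are not, and it might favour screening draws over chart values, hence patients with different prior engagement in care. A shift in the risk ratio could not be attributed to prior suppression. Its interval would be wider by 1/√(1 − share dropped): 12% with 20% dropped, 41% with half dropped. It would leave the primary result and the decision rule as they are. A fresh draw before allocation would answer the question more directly, but it costs an extra sample and assay for everyone who qualifies on a chart value.

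**Conclusion.** No change to the plan is called for. Accepting a chart value within 90 days of consent is a disclosed way of defining unsuppressed at baseline, and a reasonable trade-off in a population that is hard to enrol (the Section 17.8 simulation from pilot data gave 44 months of recruitment, against the 22 planned). Following the plan as written does not give a wrong answer: allocation is random and the test holds its 2.5% one-sided level for the patients enrolled. What remains is a matter of interpretation for the narrower group unsuppressed on the day of randomization.

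For that group the size is modest under plausible inputs: 2.8 to 4.3% instead of 2.5% when 1 to 5% are already suppressed with no arm difference among them, and 7.0% at 10%. It is 2.6 to 2.9%, and 3.4% at 10%, if the pilot's 0.82 ratio applied to them, and there is no inflation if the 0.75 ratio holds for them too. These figures rest on assumed values of f, s and r, a TAU rate of 57%, and a single-time-point normal approximation in place of the repeated-measures model.

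The month-0 wording is a clerical inconsistency. An analyst would take the screening or abstracted value as baseline, as Section 8.2 already does for the VACS Index. The interval from draw to randomization can be described by arm with the baseline data without amending the plan.

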7.2 Exclusion Criteria

Participants will be excluded if they:

- 1) Have a severe medical, psychiatric or substance use disorder that, in the opinion of the study physician, would make study participation hazardous to the participant, compromise study findings, or prevent the participant from completing the study due to imminent risk of death. Hospitalized patients who do not meet these conditions remain eligible for participation.

Examples include:

- a. Acute life-threatening medical illness (e.g., uncompensated heart failure, end-stage liver disease, acute hepatitis or moderate to severe renal impairment) as assessed by medical history, review of systems, physical exam and/or laboratory assessments;
 - b. Severe, inadequately-treated mental health disorder in need of immediate treatment (e.g., active psychosis, uncontrolled manic-depressive illness) as assessed by history and/or clinical interview;
 - c. Suicidal or homicidal ideation requiring immediate attention.
- 2) Have aspartate aminotransferase (AST) or alanine aminotransferase (ALT) liver enzymes greater than 5 times upper limit of normal on screening phlebotomy. Results from tests conducted within the past 30 days from date of consent may be abstracted from medical records.
 - 3) Have INR > 1.5 or platelet count <100k. Results from tests conducted within the past 30 days from date of consent may be abstracted from medical records.

- 4) Have known allergy or sensitivity to naloxone, naltrexone, polylactide-co-glycolide, carboxymethylcellulose, or other components of the Vivitrol® diluents.
- 5) Anticipate undergoing surgery during study participation.
- 6) Have chronic pain requiring ongoing pain management with opioid analgesics.
- 7) If female, currently (at time of consent) pregnant or breastfeeding or planning on conceiving in the coming months.
- 8) Body habitus that, in the judgment of the study physician, precludes safe intramuscular injection of XR-NTX (e.g., excess fat tissue over the buttocks).
- 9) Received methadone or buprenorphine maintenance therapy for treatment of opioid use disorder in the 4 weeks prior to consent (medically supervised withdrawal therapy is allowed).
- 10) Received ongoing XR-NTX injections as maintenance therapy for opioid or alcohol use disorder in the 4 weeks prior to consent (does not exclude individuals leaving incarceration with a single injection and no specific follow up).
- 11) Have taken an investigational drug in another study within 30 days of study consent.
- 12) Are currently in jail, prison or any overnight facility as required by court of law or have pending legal action that could prevent participation in study activities.

7.3 Recruitment

HIV-Infected Participant Recruitment:

Study participants will be recruited from participating HIV outpatient clinics. HIV clinics likely to participate in CTN-0067 typically serve as patient-centered medical homes for HIV-infected participants, offering a broad array of on-site case management, social work, and counseling support services to engage and retain patients in care. All members of the HIV clinic care team will be educated regarding the study and asked to refer potential participants who are interested in learning more about the study to clinic research staff for screening. The site PI will either be an attending HIV provider in the HIV clinic or have strong relationships with HIV providers, so we anticipate excellent cooperation in approaching potential participants. Because the study seeks to improve engagement in HIV care, the HIV clinic care team and research staff will interact with community and hospital-based outreach services to identify and engage potential participants who are not currently engaged in HIV care. Outreach to and screening of hospitalized patients is encouraged, since they represent an enriched population of people with untreated HIV and opioid use disorder. If a participant is interested in learning more about the study, a study staff member will meet with the participant to discuss the study. Potential participants will be briefly instructed regarding opioid agonist and antagonist therapy and complete a survey demonstrating understanding as part of the consent process prior to enrollment. Specific recruitment procedures (e.g., local educational activities, community outreach, print- and web-based advertisements, etc.) will vary by site according to local needs. Strict ethical guidelines regarding professional conduct and confidentiality will be enforced for all study staff. Particular populations of interest to be targeted for recruitment include:

- Hospitalized patients. HIV outpatient clinic sites will be encouraged to partner with their affiliated inpatient institutions for recruiting these patients.

- Emergency Departments (EDs). Clinics will be encouraged to partner with local EDs for direct referral of patients presenting to the ED with opioid overdose.
- Persons utilizing local needle exchange and other sites that provide HIV testing for persons who inject opioids.
- Detox/addiction treatment facilities with HIV testing services.
- Local syringe exchange programs.
- People receiving services from community-based AIDS service outreach organizations.
- People being released from local criminal justice systems.

Enrolling participants in clinical settings poses many challenges to screening and interviewing potential participants [120-123], including the rapid pace of care, interruptions, clinic productivity requirements, space limitations, participants not feeling well enough, and the presence of multiple HIV care team staff members. To minimize the impact of these challenges, research staff will spend considerable time in participating HIV clinics interacting with staff, familiarizing themselves with clinic patient flow, and learning how to communicate and negotiate with clinic staff regarding the necessary space and time to conduct interviews.

Site PIs, who are HIV clinic providers or someone who has strong relationships with HIV providers, will facilitate negotiation of space and time requirements and be a resource to research staff regarding participating HIV clinic procedures. Staff and sites with experience and expertise in conducting research studies in outpatient HIV clinic settings will be prioritized for site selection. A review of 13 clinical trials conducted in the University of North Carolina Infectious Disease Clinic suggested that integrating a dedicated research screener in clinic operations facilitates trial enrollment [123]. The Lead Investigator's research team has experience successfully integrating clinical trial research teams with outpatient HIV clinic staff, enrolling 82% of HIV providers and 73% of their eligible participants in one recent trial [122].

The interviewer will negotiate the location of the interview as necessary to protect confidentiality and respect HIV clinic patient flow. If necessary, the potential participant will be given the option to participate in screening, consent, and interview procedures in a nearby exam room or staff/patient lounge if it is unoccupied, or to reschedule the interview at another time. If a participant feels ill during the interview, the interview will stop and be rescheduled. In the Lead Investigator's team's prior experience conducting research interviews in outpatient HIV clinics, the team found this level of flexibility achieved high levels of participation and did not impede the flow of usual HIV clinic activities [3, 29, 124].

Participants may undergo repeat screening within the appropriate amount of time after an initial screen-fail, per the discretion of the site PI and in accordance with the Manual of Operating Procedures.

